#### 8.1.3.4 Observed case analysis

This analysis will only include the observed data for subjects still on the original double-blind study treatment. Subjects with missing ASDAS data at Week 52 will not be included in the

analysis and hence only a subset of subjects will be analyzed and no composite endpoint implemented. The same logistic regression model specified for the primary efficacy analysis will be performed. The odds ratio and corresponding 95% CI of the ASDAS-MI responder rates at Week 52 based on the observed data will be estimated and tested between treatment groups using a logistic regression model with factors of treatment group, region, and MRI/CRP classification (MRI+/CRP+; MRI+/CRP-; MRI-/CRP+).

## 8.2 Statistical analysis of secondary efficacy variables

The secondary efficacy variables are designated as variables 2 through 11 in the hierarchical testing procedure outlined in [Section 8](#), in addition to counts of relevant changes to background medication. The statistical methodology to be used for the analysis of these variables is described below.

### 8.2.1 Derivation of secondary efficacy variables

#### 8.2.1.1 Assessment in Axial SpondyloArthritis international Society response criteria (ASAS20/40, ASAS5/6, and ASAS partial remission)

The ASAS20 response is defined as an improvement of at least 20% and absolute improvement of at least 1 unit on a 0 to 10 NRS in at least 3 of the 4 following domains (Anderson, 2001):

- Patient's Global Assessment of Disease Activity;
- Pain assessment (the total spinal pain NRS score);
- Function (represented by the BASFI);
- Inflammation (the mean of the BASDAI questions [Q] 5 and 6) concerning morning stiffness intensity and duration)

and absence of deterioration in the potential remaining domain [deterioration is defined as a relative worsening of at least 20% and an absolute worsening of at least 1 unit].

ASAS data collected after the discontinuation of double-blind study treatment will be treated as missing in the original data set.

The ASAS criteria for 40% improvement (ie, ASAS40) are defined as relative improvements of at least 40% and absolute improvement of at least 2 units on a 0 to 10 NRS in at least 3 of the 4 domains and no worsening at all in the remaining domain.

The ASAS 5/6 response is defined as at least 20% improvement in 5 of 6 domains, which includes spinal mobility (i.e., lateral spinal flexion of the BASMI) and CRP as more objective measures (Brandt et al, 2004). For CRP values below the lower limit of quantification (<4mg/L), half the lower limit (2 mg/L) will be used as the imputed value.

The ASAS partial remission response is defined as a score of  $\leq 2$  units on a 0 to 10 unit scale in all 4 domains.

ASAS40 response at Week 12 and Week 52 are secondary efficacy endpoints.

#### 8.2.1.2 Bath Ankylosing Spondylitis Disease Index (BASDAI)

The BASDAI is the most commonly used instrument to measure the disease activity of ankylosing spondylitis. The BASDAI is a validated self-reported instrument which consists of 6

horizontal NRSs, each with 10 units to measure the severity of the 5 major symptoms: fatigue, spinal pain, peripheral joint pain and swelling, enthesitis, and morning stiffness (both severity and duration) over the last week. To give each symptom equal weighting, the average of the 2 scores relating to morning stiffness is taken. The resulting 0 to 50 sum score is divided by 5 to give a final BASDAI score between 0 and 10, with lower scores indicating lower disease activity.

If 1 of the 2 morning stiffness measurements (ie, questions: “How would you describe the overall level of morning stiffness you have had from the time you wake up?” and “How long does your morning stiffness last from the time you wake up?”) is missing, the other one will be used for the morning stiffness calculation. The same imputation is also applied for the calculation of the ASAS inflammation component, which is calculated as the average of the 2 morning stiffness measurements.

If 1 major symptom of the BASDAI is missing, the sum score of the remaining symptoms will be divided by the number of symptoms assessed. If more than 1 major symptom is missing, the sum score will be set to missing.

The BASDAI data collected after the discontinuation of double-blind study treatment will be treated as missing in the original data set.

The BASDAI50 response is defined as an improvement of at least 50% in the BASDAI compared to Baseline.

Change from Baseline in BASDAI at Week 12 and Week 52 are secondary efficacy endpoints.

#### **8.2.1.3 Bath Ankylosing Spondylitis Functional Index (BASFI)**

The BASFI contains 10 questions. The first 8 questions evaluate activities related to functional anatomical limitations due to the course of this inflammatory disease. The final 2 questions evaluate the subjects’ ability to cope with everyday life. An NRS ranging from 0 to 10 is used to answer the questions on the test.

The mean of the 10 scales gives the BASFI score, which is a value between 0 and 10.

In case of missing answers to 1 or 2 of the single items within the BASFI questionnaire, the BASFI score will be calculated by imputing missing items with the mean of the completed items. Then, the BASFI score will be calculated as described above. If more than 2 of the items are missing, the BASFI score will be left missing.

The BASFI data collected after the discontinuation of double-blind study treatment will be treated as missing in the original data set.

Change from Baseline in BASFI at Week 12 and Week 52 are secondary efficacy endpoints.

#### **8.2.1.4 Magnetic Resonance Imaging (MRI) assessments**

The SPARCC scoring method for lesions found on the MRI is based on an abnormal increased signal on the short-tau-inversion recovery (STIR) sequence, representing bone marrow edema (defined as an increased signal in bone marrow on a T2-weighted sequence, reflecting an increased concentration of “free water” related to a bone lesion). Each SI joint is divided into 4 quadrants: upper iliac, lower iliac, upper sacral, and lower sacral. The presence of increased signal on STIR in each of these 4 quadrants is scored on a dichotomous basis, where 1 =

increased signal and 0 = normal signal. Joints that include a lesion exhibiting intense signal are each given an additional score of 1 per slice that demonstrated this feature. Similarly, each joint that included a lesion demonstrating continuous increased signal of depth greater or equal 1 cm from the articular surface is also given an additional score of 1. The scoring is repeated in each of 6 consecutive coronal slices. Total SI joint SPARCC scores can range from 0 to 72.

The Berlin modification of the ASspiMRI-a is a scoring system with a concentration on STIR sequences without other fat saturation techniques. This scoring method quantifies active changes in 23 vertebral units (VU) of the spine (from C2 to S1). A VU is defined as the region between 2 virtual lines through the middle of each vertebra. Active inflammation is scored by grading the degree of bone marrow edema from 0 to 3 in 1 dimension on 1 or more consecutive slices that represent the highest level of inflammation in a particular VU. Total spine ASspiMRI-a score in the Berlin modification can range from 0 to 69.

The following imputation rules should be used for calculating the total for both SI joint SPARCC scores and spine ASspiMRI-a score in the Berlin modification:

- If all scores are NA at a visit, the imputed total is blank for that visit.
- Treat NA as 0 when computing the total score.
- Carry the NA score from the Baseline visit forward to all post-Baseline visits unless all scores at Baseline are NA.
- Carry the numeric score from the last visit with non-NA score forward if a score is NA at a post-Baseline visit (unless all scores are NA post-Baseline).
- If ALL the Baseline scores are NA, then do not carry forward the Baseline scores. Treat the subsequent visit as a surrogate Baseline.

The details related to how the MRI data will be read and adjudicated will be outlined in a separate imaging charter. In the cases where the initial two readings are discrepant, a third reading is performed by an independent reader. This third score is not an adjudication but rather an additional score and value for analysis which will be based on the average of all 3 reader assessments. There will also be two sessions of readings. The first session will conduct readings of the Baseline and Week 12 MRI and will be used for summaries at Week 12. The second session will conduct readings of the Baseline, Week 12 and Week 52 MRIs and will be used for summaries at Week 52.

The following visit windows will be applied:

- All Baseline values should be collected prior to randomization as MRI is required to be randomized into the study.
- With the exception of Week 156, for post-Baseline visits, a time window of 2 weeks before or after the scheduled visit will be used for mapping MRI data to the given visit.
- For Week 156, a time window of 4 weeks before or after the scheduled visit will be used for MRI data to the given visit. The expected day for Week 156 will be calculated assuming that the SFE period start was on Week 52. I.e. Week 156 will be expected to be  $(156-52) \times 7$  days after Week 52. For patients where the first dose after the Week 50 is before the SFE informed consent the width of the lower boundary of the Week 156 window will be increased further

by the absolute number of days between the first dose after the Week 50 visit and the SFE informed consent date.

The SI joint SPARCC data collected after the discontinuation of double-blind study treatment will be treated as missing for any observed case analysis.

The change from Baseline in SI joint SPARCC score at Week 12 is a secondary efficacy endpoint.

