## **3 DATA ANALYSIS CONSIDERATIONS**

### **3.1 General presentation of summaries and analyses**

All statistical analyses will be performed using SAS® (STATISTICAL ANALYSIS SYSTEM, SAS-Institute, Cary, NC, USA) according to UCB SOPs.

For continuous data in general, summary statistics (n [number of available measurements], arithmetic mean, SD, median, minimum, and maximum) will be presented by treatment group. For selected variables, the first (25th percent) quartile (Q1) and the third (75th percent) quartile (Q3) may also be presented (for patient reported outcomes).

Mean, SD, median and quartiles will be displayed to 1 more decimal place than collected in the source data. Derived variables in general will display the mean, SD and median to 1 more decimal place than the variables used in the derivation (i.e. a change from Baseline will be reported to the same precision as the Baseline data). However, a special rule can be defined as needed for appropriate reporting.

For descriptive statistics of continuous variables by visit, the change from Baseline and actual value at the given time point will be displayed. The change from Baseline is the post-Baseline value minus the Baseline value. If the Baseline or post-Baseline value is missing, then the change from Baseline is set to missing. Percent change from Baseline is the change from Baseline divided by Baseline and multiplied by 100. If the Baseline value is 0 and the post-Baseline value is also 0, then the percent change from Baseline is set to 0. If the Baseline value is 0 and the post-Baseline value is non-zero, then the percent change from Baseline is set to missing. If the Baseline value is missing, the percent change from Baseline is set to missing.

Frequency tables (frequency counts and percentages) will be presented for categorical data. If there are no missing values then the missing row can be removed. If there are missing values (including missing a single assessment or entire visit), then include the missing row with the frequency count and percentage. If there are no subjects in a specific electronic case report form (eCRF) category, then that row will be retained and 0 presented in the table.

In general, percentages will be calculated based on the utilized analysis set. However, in the case of subgroup analyses, the N of the subgroup will be used as denominator.

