### 3.3 Definition of Baseline values

Unless otherwise specified, the last valid measurement before study medication administration in the double-blind period will be used as the Baseline value. The same Baseline definition will be used for the open-label period and SFE period. For almost all variables, this will be the assessment made at the Baseline visit. However, for some variables (eg, demography) assessments are scheduled for the Screening visit only and not for the Baseline visit. In this case, the Screening value will be utilized as Baseline value. If a Baseline visit measurement is missing, and a Screening visit measurement is available, the Screening value will be utilized as Baseline. If a scheduled Baseline assessment is taken on the same day as first administration of study medication and no time is collected, it will be assumed to have been taken prior to study medication.

Baseline images, either spinal x-ray or MRI assessments, are required to evaluate study eligibility. Therefore, all Baseline images will be available prior to randomization into the study. SI joint x-rays should not be older than 12 months prior to Baseline and should be verified by central reading during the Screening period.

There will be an additional SFE Baseline presented in some tables. It is defined as the last value before the patient received SFE treatment (the first dose on or after SFE informed consent, for most patients this will be the Week 52 value).

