3. For each completed data set, the outcome (response or change from Baseline) will be calculated using the complete datasets (with no missing data).
4. For ASAS40, complete parts 5 and 6 from [Section 8.1.3.2](#) in order to provide odds ratios, 95% CIs and the p-value from the proc mianalyze. For BASDAI, BASFI, SI joint SPARCC, ASQoL and Nocturnal Spinal Pain, complete parts 4 and 5 from [Section 8.2.2.2](#) in order to provide treatment differences, 95% CIs and the p-value from the proc mianalyze.

Additionally, change from Baseline in SI joint SPARCC score at Week 12 is a continuous secondary efficacy variable. The same referenced based multiple imputation procedure specified in this section will be used to account for missing SPARCC data. However, it should be noted that, unlike BASDAI and BASFI, SPARCC score will not be measured at any time points between Baseline and Week 12, meaning that those are the only 2 time points that can be considered in the evaluation of SPARCC score at Week 12. Comparisons between treatment groups will be made using an analysis of covariance (ANCOVA) model on the imputed data set. The model will include Baseline score, treatment group, region, and MRI/CRP classification.

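### The MRI scoring rules let the first post-dose image stand in as Baseline without saying for what purpose; taken literally, this gives a Week 12 SPARCC change of zero and an on-treatment Baseline covariate

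*SAP*

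**What the plan says.** Section 8.2.1.4 gives a list of rules with this introduction: "The following imputation rules should be used for calculating the total for both SI joint SPARCC scores and spine ASspiMRI-a score in the Berlin modification". Three of them matter here.

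- The first rule: "If all scores are NA at a visit, the imputed total is blank for that visit".
- The third rule carries Baseline NA positions forward to later visits, except where the whole Baseline is NA.
- The last rule deals with that exception: "If ALL the Baseline scores are NA, then do not carry forward the Baseline scores". It then adds: "Treat the subsequent visit as a surrogate Baseline".

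Three other sections bear on how the last rule would be applied.

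- Section 3.1 defines change as the post-Baseline value minus the Baseline value and adds: "If the Baseline or post-Baseline value is missing, then the change from Baseline is set to missing".
- Section 3.3 gives the general definition, with an opening allowance for exceptions specified elsewhere: "the last valid measurement before study medication administration in the double-blind period will be used as the Baseline value".
- Section 8.2.2.2, on the Week 12 SPARCC endpoint, states: "SPARCC score will not be measured at any time points between Baseline and Week 12". It concludes: "those are the only 2 time points that can be considered in the evaluation of SPARCC score at Week 12". The ANCOVA there adjusts for Baseline score, treatment group, region and MRI/CRP classification.

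In Section 8, change in SI joint SPARCC at Week 12 is test 8 in both testing sequences and precedes tests 9 to 11.

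**The concern.** The surrogate is called a Baseline without qualification, so a programmer could reasonably use it wherever the analysis needs a Baseline value. That includes the change score, the ANCOVA covariate and the Baseline SPARCC subgroup (<5, ≥5) that Section 4.8 applies to the primary endpoint. In each place a score measured after randomized treatment would replace a pre-treatment one.

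For test 8, an affected subject would contribute a change that carries no information about treatment, together with a covariate that treatment can influence. For the Week 52 and Week 156 SPARCC changes and the Week 52 ASspiMRI-a change, whatever happened in the first 12 weeks would be lost for that subject. The Week 52 analyses lie outside the multiplicity-controlled sequence (Section 8.3) and the Week 156 summaries are descriptive (Section 8.4), so the confirmatory consequence is confined to test 8 and the tests after it.

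**Working it through.** **The plan's own figures.** The SAP gives no assumed effect, variability or NA rate for SPARCC, so there is no endpoint-specific figure to reproduce. The stated score ranges do follow from the scoring description. SPARCC is 6 slices × 2 joints × (4 quadrants + 1 intensity + 1 depth) = 72. The Berlin score is 23 vertebral units × 3 = 69. The sample-size statement in Section 2.4 concerns the primary endpoint and does not enter this point.

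**What the literal rule produces.** Let B be the Baseline total and W the Week 12 total, for a subject whose Baseline is all NA and whose Week 12 image is readable and in window.

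1. By Section 8.2.2.2 there is no SPARCC measurement between Baseline and Week 12, so the subsequent visit is Week 12.
2. By the last rule of Section 8.2.1.4, B is replaced by W.
3. By Section 3.1, change = W − W = 0, whatever W is.
4. By Section 8.2.2.2, the Baseline covariate is W.

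If Week 12 is also all NA, the next visit is Week 52. The Week 52 change is then the one set to zero, and there is no Week 12 value.

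**What the other reading produces.** Under the first rule of the same list, B stays blank. Under Section 3.1 the change is then missing. No artificial zero arises, and no post-dose value enters the covariate.

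**Size in unadjusted means.** If a fraction p of each arm is affected at random, the difference in mean change becomes (1 − p) × the true difference. For p = 2% to 5% that is a 2% to 5% reduction.

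**Size under the planned type of model.** A simulation fitted an ANCOVA of change on treatment and Baseline, without region or MRI/CRP class. None of its SPARCC inputs comes from the SAP:

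- 150 subjects per arm (the planned size), 2,000 replicates
- Baseline normal with mean 9 and SD 12, truncated to 0–72
- Week 12 = 2.5 + 0.6 × Baseline − 4 if on CZP + residual with SD 6, truncated to 0–72
- Baseline NA at random, at the same rate in both arms

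With no NA the average estimate is −3.16; truncation pulls it in from −4.

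| Share with all-NA Baseline | Subjects of 300 | Surrogate rule | Affected subjects left out | Attenuation |
|---|---|---|---|---|
| 1% | 3 | −3.125 | −3.141 | 0.016 / 3.141 = 0.5% |
| 2% | 6 | −3.102 | −3.132 | 0.030 / 3.132 = 1.0% |
| 5% | 15 | −3.062 | −3.146 | 0.084 / 3.146 = 2.7% |
| 10% | 30 | −2.963 | −3.137 | 0.174 / 3.137 = 5.5% |

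Under these inputs the adjusted estimate loses roughly half of p, less than the unadjusted formula gives.

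**The case against.** The strongest reply is that the rule concerns something else. The list is introduced as rules for computing totals. The last rule completes the third: normally the Baseline NA pattern is carried forward, and where all of Baseline is NA a different reference visit is needed. On that reading the surrogate only resets the item-level pattern, the Baseline total stays blank and the change is missing. The first rule and Section 3.1 both point this way. This reading may well be what was intended, so it would be too strong to say that the SAP certainly forces a zero change. The text still does not restrict the surrogate to that use, and the literal reading remains open.

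A reader might also infer a contradiction with Section 3.3. The documents do not support that. Section 3.3 applies unless something else is specified, and an MRI-specific rule can be such an exception. That makes the rule permissible in form; it does not make a post-dose score a sound Baseline.

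The trigger should also be rare. Section 2.3.1 requires a central MRI reading by the Baseline visit, and Sections 3.3 and 8.2.1.4 place all Baseline images before randomization. This stands as an argument about size. It does not empty the case. An image can exist and still be scored NA throughout, Baseline is read again in a second session, and Section 4.8 itself foresees a missing second reading. MRI eligibility rests on sacroiliitis, so it does not guarantee a scorable spine.

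**Conclusion.** The point stands as an unrestricted rule that, taken literally, yields wrong values in a multiplicity-controlled endpoint. For each affected subject with a readable Week 12 MRI, the whole Week 12 SPARCC change is replaced by zero and the Baseline covariate is an on-treatment score. This follows from Sections 8.2.1.4, 3.1 and 8.2.2.2 without further assumptions.

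The aggregate effect is probably small. The number of affected subjects is not given. Under the assumed simulation inputs the adjusted difference is attenuated by about 0.5% to 3% when 1% to 5% are affected. The direction is toward zero, against CZP, provided NA occurs at random and equally in both arms.

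One might infer that the rule strips most of the drug effect from the Week 52 and Week 156 changes because improvement comes early. The SAP says nothing about when CZP subjects improve, so only the weaker statement holds: those changes would start from a treated image.

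**What to change.** Replace the open-ended instruction in Section 8.2.1.4 with a limited one:

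- The surrogate visit serves only as the reference for carrying forward item-level NA scores.
- The Baseline total stays missing. Either the change is missing under Section 3.1, or the Baseline is imputed from pre-randomization data only. State which, because Section 8.2.2.2 does not say whether a blank Baseline falls under its step for intermittent missing scores.
- No post-dose image is used as a Baseline value, covariate or subgroup classifier.

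Report the number of affected subjects by arm, for SPARCC and ASspiMRI-a separately.

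Two simpler remedies are less suitable. Deleting the rule would leave the third rule's exception without a reference visit. Substituting another reader's Baseline score may conflict with the imaging charter to which Section 8.2.1.4 refers reading and adjudication.

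The cost is a few sentences and one count. Sections 2.2.1.3 and 8.1.1 show that the double-blind outputs already exist, so the clarification should be documented as made after the Week 52 lock. If the count is zero, nothing else changes. If any subject is affected for Week 12 SPARCC, rerun that analysis and show it beside the reported result.
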